**Change in protocol 7.12.2018 (all sites)**

- Assessment 4 will be the final assessment for both Active and Sham. Subjects originally on Sham will be offered 12 weeks of Active treatment, instead of 24 weeks of Active treatment
- Assessment 5 is removed from protocol

- **The maximum compensation for both Active and Sham is \$280**

**Data Management.** Data processing and management will be conducted in the Center for Research and Evaluation (CRE) at the University of Pittsburgh under the supervision of [name], Director of CRE and co-investigator for this project. The CRE also provides support for form design, data entry and verification, programming, and data management as fee-for-service. The CRE supports the design and implementation of paper-and-pencil, computer-based and web-based data collection forms.

The CRE will serve as the data processing center for all data collected. Form design and data management will be conducted in the CRE under the supervision of [name], Director of CRE and co-investigator/statistician for this project. Oracle (version 11g, Oracle Corp., Redwood Shores, CA) will be used for data management. Data will be collected in three forms: paper-and-pencil instruments, electronic monitors, and biological values. For paper-and-pencil instruments, Teleform Elite (version 10, Verity, Inc., Sunnyvale, CA), a Windows-based software package for automated data entry/verification, will be used for form design, data entry, and data verification.

For each form, the corresponding Oracle database tables will be initialized for automatic data exportation, and data dictionaries will be created. Following data collection all forms will be thoroughly screened for completeness of response upon receipt and scanned into the database; therefore, we anticipate that there will be very little missing data due to oversights in collection. During verification, erroneous responses will be checked with the source documents and corrected before proceeding with further verification. Using the data dictionaries and data editing programs, final range checking and contingency checking of responses will be accomplished. After this final data cleaning, summary indices and scales will be computed, and the data files for statistical analysis will be created. Data collected using electronic data capture methods (SenseWear Pro Armband®) will be uploaded from the devices to the project computer, interpreted using the software, exported as an ASCII file, and merged with identifying information into the Oracle database. The biological data will be entered in an Excel file at the laboratory then merged with the project's Oracle database. The Oracle database is maintained on an off-site centralized server housed at the Network Operating Center (NOC) of the University of Pittsburgh. The NOC is a secure, high availability University facility equipped with backup power, redundant networking, heating, and cooling, 24-hour staffing, and a data mirror system to create continuous backups.

Data collection at West Virginia University will be performed by the study team with verification and oversight provided by PI, [name]. De-identified data from VAPHS and West Virginia University study participants will be sent to [name] office at the University of Pittsburgh.

## C. STATISTICAL ANALYSIS

Data will be analyzed using SAS (version 9.3., SAS Institute, Inc., Cary, NC) to conduct exploratory data analyses, missing data estimation, and repeated measures modeling. Mplus (version 6.12, Muthén & Muthén, Los Angeles, CA) will be used for the fitting of mediational models to explore mechanistic pathways. When screening data, the level of significance will be set to .05 for two-sided hypothesis testing. Although directional hypotheses have been posited for the endpoints associated with the primary aims, a more conservative approach will be adopted and hypothesis testing will be nondirectional. Given the multiple endpoints and time points to be examined for the primary aims, the testwise level of significance will be set at .01 to limit the inflation of type 1 error. Confidence intervals for point estimates will be computed at 99%.

**Preliminary Analyses.** Detailed exploratory data analyses will first be performed, involving data description and data screening for anomalies (e.g., outliers, nonnormality, etc.). The results from this initial investigation will be used to: 1) describe univariate and bivariate data distributions; 2) identify imbalances between treatment groups and associations between the dependent variables and suspected covariates/confounders); 3) evaluate the amount and patterns of missing data; and 4) check for the violation of statistical assumptions for the planned analyses. Covariates/confounders will be included in models secondarily and their effect on the results of primary predictors/factors will be evaluated. The randomness of missing data will be investigated using available information on subject characteristics to help discern patterns in the missing data, identify the possible covert missing data mechanisms, and inform the choice of the strategies to handle missing data. It is anticipated that the primary reason for data to be missing will be subject attrition. We will closely monitor attrition and conduct logistic regression models via SAS PROC LOGISTIC to compare the characteristics of participants who remained in the study versus those who dropped out to determine if data are missing at random. If the data are missing at random (i.e., not related to the outcome itself), likelihood estimation procedures, such as those used in SAS PROC MIXED, GLIMMIX and NLMIXED as well as Mplus, will produce unbiased estimates while allowing us to retain cases with missing values on the outcome variables. If needed, multiple imputation would be used to impute missing values on the predictor variables. If the data are not ignorably missing, we use pattern mixture or selection modeling to examine data attrition.

Data Analysis Plan for Primary Aim 1. An "intent-to-treat" (ITT) approach will initially be used during data analysis when investigating efficacy of CPAP+DEC compared to sham-CPAP+DEC. All subjects will be included in the data analysis in the groups to which they were randomly assigned, regardless of the adherence to protocol, treatment received, withdrawal or deviation from protocol. Adherence with the assigned protocol, will be monitored throughout the duration of the study. With this ancillary information, the sensitivity of the results under the ITT model will be explored to identify the effects of the amount of intervention received and the deviations in protocol on the efficacy of the interventions. Since the primary endpoint of interest, glycemic control, is assessed repeatedly using two measures, fructosamine and A1C, linear mixed modeling (LMM) with linear contrasts to test the stated hypotheses. A flexible modeling approach, mixed modeling allows for unequally spaced assessments, fixed and time-varying covariates, dependent variables with data that are missing at random, and modeling the covariance/correlation among longitudinal responses. We will consider the baseline value both as an assessment point as well as a possible covariate in analyses. The primary independent variable is the randomized assignment to treatment (CPAP+DEC vs. sham-CPAP+DEC). Fixed and/or time-dependent covariates (including baseline outcome values) may be included in the repeated measures model as indicated secondarily based on the results on the preliminary data analysis to adjust for group imbalances or variables related to the dependent variable. Prior to fitting the repeated measures model, the structure of the estimated covariance matrix for the repeated measures will be carefully examined to determine the appropriate covariance structure. Fit indices will also be used to evaluate the repeated measures models estimated assuming different covariance structures to identify the most appropriate covariance structure. When fitting models, time will be treated as a fixed, repeated within-subjects factor, while treatment assignment will be a fixed, between-subjects factor, with an interaction between time and group. F-tests will be used to test the main and interaction effects included in the model. Individual regression parameters will be computed and reported with their asymptotic standard errors to yield confidence intervals. Sensitivity analyses will be performed to discern the impact of influential cases on results. To test the associated hypothesis (H1), linear contrasts will be specified and estimated when fitting the repeated measures model to compare, relative to baseline values, the CPAP+DEC and sham-CPAP+DEC groups on: 1) the 6-week values of fructosamine and A1C and the 2) 12-week values of fructosamine and A1C. Wald t-statistics will be used to test each linear contrast. Confidence intervals will be obtained for these linear contrasts. Marginal modeling with generalized estimating equations will also be used as it tends to be more robust to misspecification of the covariance structure of repeated assessments and violations in the normality assumption for continuous outcomes.

Analysis Strategy for Aim 2. Using the approach described for Aim 1, repeated measures models will be fitted, and linear contrasts will be estimated to compare 6-week and 12-week values for improvements in diabetes self-management outcomes (retention of information taught during the DEC classes [DKT], improved self-management behaviors [SDSCA], increased physical activity [SenseWare Armband steps], and decreased diabetes-related distress [PAID]) relative to baseline values between subjects on CPAP+DEC and those receiving sham-CPAP+DEC. Generalized linear mixed modeling or nonlinear mixed modeling will be used to analyze longitudinal categorical outcomes should outcome variables need to be categorized for analysis. Along with test statistics and p-values, point and interval estimates will be obtained for linear contrasts.

Analysis Strategy for Aim 3. We will *explore* adherence to CPAP (dose) and specific neuro-behavioral and physiological mechanisms (nighttime sleep, daytime sleepiness, mood, and vigilance during DEC sessions) as possible intervening, or mediator, variables that may mediate the effects of CPAP treatment on glycemic control and diabetes self-management outcomes. Initially, we will fit simple mediational models (predictor, single mediator, single outcome) and estimate whether the effects of CPAP (predictor) on changes in glycemic control and diabetes self-management outcomes are mediated through changes in specific neuro-behavioral and physiological variables (i.e., nighttime sleep, daytime sleepiness, mood, and vigilance during DEC sessions). Standardized parameter estimates of path linkages (with confidence intervals) will be obtained to summarize associations between the exogenous treatment variables, suspected mediators, and distal outcomes, as well as the indirect effect of the treatment group on the targeted outcomes through the suspected mediators and the direct effect of the treatment group on the outcomes. The goodness-of-fit of a model will be assessed using standard summary indices (e.g., RMSEA, CFI) as well as through residual analyses. Depending on the results for testing of individual mediators, we may combine the mediators into a multiple mediator model to develop a more complete picture of these hypothesized mechanisms of action for CPAP.

Analysis Strategy for Aim 4. For this aim we will combine the 6 months of data for the two groups receiving CPAP (including the participants in the delayed treatment group who crossover to CPAP) to *explore* retention of treatment effects and to explore the association between the durability of treatment of OSA (i.e. adherence to CPAP) and 1) sleep

quality [PSQI], 2) daytime sleepiness [ESS], 3) mood [POMS], 4) diabetes self-management [SDSA, DES-SF, PAID7, and 5) glycemic control [fructosamine and A1C] after 24 weeks of active CPAP. For delayed treatment group participants, the initial assessment for this analysis will be their assessments at 12 weeks from study start. Random coefficient modeling will be applied to model changes in sleep quality, daytime sleepiness, mood, diabetes self-management and glycemic control and to associate these changes with objectively measured CPAP adherence via the EncoreAnywhereTM. Estimated regression coefficients and confidence intervals will be reported to summarize changes in outcomes over time and their associations with CPAP adherence.

**Sample Size Justification.** The study sample size of 210 was determined focusing on the testing of hypotheses associated with the primary aims (Hypotheses 1 and 2) and considering the results of the pilot/feasibility study (reported in Approach), the adjustment of the testwise significance level to .01 to limit inflation of type 1 error due the multiple testing of hypotheses at 6- and 12-weeks follow-up for several outcomes, and the anticipated subject attrition during the 12-weeks of follow-up. Regarding Aim 1, our pilot/feasibility study suggests that CPAP improves glycemic control as measured by serum fructosamine (see Table 1). Therefore, we anticipate large effects (in terms of standardized mean differences,  $d$ ) on the order of  $d = -0.74$  may be detected with 0.80 power with a group sample size of 48 (96 total) when comparing mean changes from baseline to 6 weeks and to 12 weeks in serum fructosamine between CPAP+DEC and sham-CPAP+DEC groups using linear contrasts from a repeated measures model at testwise two-tailed level of significance of .01. Regarding Aim 2, we have observed effect sizes with magnitudes ranging from 0.22 to 1.27 (median effect size of 0.75) for 4-week changes from baseline in physical activity, sleep, vigor, fatigue and vigilance measures (see Table 1). Groups of 84 participants (168 total) will be of sufficient size to detect effect sizes as small as  $d = 0.53$  in mean changes from baseline to 6 weeks and to 12 weeks (based on linear contrasts from a repeated measures model) with 0.80 power at testwise two-tailed level of significance of .01. Although efforts will be made to retain study subjects, some subject attrition is possible. Our recent pilot/feasibility study of active-CPAP with a 4-week follow-up in adults with type 2 diabetes demonstrated low attrition of 5%. In the CATNAP study ([name] et al.) about 10% attrition was observed. To ensure an adequate number of subjects complete the study by conservatively adjusting sample size for 20% attrition, we plan to enroll 210 subjects (105 per group) to have at least 168 subjects (84 per group) complete the study.

**Potential Challenges and Strategies.** We anticipate two potential problems: 1) management of a large-scale study and 2) loss of blinding by research staff involved in data collection. Our strategies are that [name] has the support of a cohesive team of co-investigators who are recognized in their areas of knowledge and have complementary expertise to this project. Our pilot/feasibility study demonstrated that study protocol successfully blinded subjects. We have developed a diagram of study personnel (see Appendix), duties, and blinding status to demonstrate how we plan to maintain blinding. We are aware that reducing subject burden is important. Although we did not have complaints of excessive burden in the pilot study and a 95% retention rate, we have further minimized burden with: 1) home testing of OSA with the ApneaLinkPlus® and 2) consolidating study activity to eliminate a separate discharge/exit evaluation. The two diabetes education sessions are part of standard diabetes care and the one-to-one format is more time efficient than regular group classes. The study sites (UPMC and VAPHS) are accessible by bus and we provide free parking to study participants. We will monitor seasonality as a potential confounder. We have the team and resources in place to implement this vitally significant study that will elucidate the role of sleep disorders as a previously unrecognized but significant barrier to the management of chronic disease.

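### The comparison of drop-outs with completers cannot tell MAR from MNAR, so the MNAR sensitivity analysis of the H1 contrasts should not be conditional on it

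*Combined protocol and SAP*

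**What the plan says.** Section C, Preliminary Analyses, expects attrition to be the main cause of missing data. It plans a logistic regression "to compare the characteristics of participants who remained in the study versus those who dropped out to determine if data are missing at random". It also plans a wider look at missing-data patterns, using what is known about the subjects, to "identify the possible covert missing data mechanisms, and inform the choice of the strategies to handle missing data".

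Two branches follow:

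- The likelihood branch opens with "If the data are missing at random (i.e., not related to the outcome itself" and describes those methods as unbiased.
- The other branch reads: "If the data are not ignorably missing, we use pattern mixture or selection modeling to examine data attrition".

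The opening paragraph of Section C adds: "When screening data, the level of significance will be set to .05 for two-sided hypothesis testing". Tests for the primary aims use .01.

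The Data Analysis Plan for Primary Aim 1 keeps every subject in the assigned group "regardless of the adherence to protocol, treatment received, withdrawal or deviation from protocol" and fits a linear mixed model whose stated basis is MAR. H1 is tested by contrasts on A1C and fructosamine at 6 and 12 weeks. The further checks there concern adherence and protocol deviations, influential cases ("Sensitivity analyses will be performed to discern the impact of influential cases on results"), and a marginal model chosen for robustness to the covariance structure and to non-normality.

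**The concern.** MAR and MNAR differ only in whether drop-out depends on the unobserved outcome once the observed data are taken into account. A regression of drop-out on observed characteristics says nothing about that. The wider review of patterns uses observed information too. So the plan gives no valid basis for choosing between its two branches.

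If the check is read as supporting MAR, the plan calls for no MNAR analysis. If one is run, its stated target is attrition, and no H1 contrast is named. The other Aim 1 checks do not address outcome-dependent drop-out.

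This matters because withdrawn subjects stay in the intention-to-treat analysis, and where their 12-week value is missing, their contribution rests on MAR. The documents give one route by which MAR could fail differently by arm. Protection Against Risk (Section D) withdraws subjects who report falling asleep at the wheel, and Aim 3 names daytime sleepiness as a possible mediator of the CPAP effect on glycemic control. That route points mainly to sham-arm drop-out and so to an understated CPAP effect.

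**Working it through.** **1. The plan's own figures (Sample Size Justification).** With d = 0.53, two-sided alpha .01 and power .80, n = 2(2.576 + 0.842)² / 0.53² = 83.2, so 84 per group. Then 168 / 0.80 = 210. Both reproduce. The allowance of 20% is 42 of 210 subjects. The same section reports 5% attrition in the 4-week pilot and about 10% in an earlier sham-CPAP trial.

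**2. What the check can estimate.** Let R mark drop-out before week 12. The regression estimates P(R | arm, baseline, other observed values). MAR is the statement that P(R | those values, 12-week value) does not depend on the 12-week value. That value is absent whenever R = 1, so models with and without the dependence can fit the observed data equally well. A significant regression is evidence against MCAR only. Adding 6-week values does not change this.

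**3. Simulation (assumed inputs).**

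- Data: 2,000 trials per scenario, 105 per arm, unit variance. Correlations were .8 (0-6 weeks), .85 (6-12) and .7 (0-12); the 20% one-arm runs were repeated with all at .7.
- Drop-out: driven by the part of the 12-week value not explained by baseline, with log-odds 0.5 or 1.2 per SD. The other arm had the same drop-out rate, completely at random.
- Timing: none, half or all of the drop-out before week 6 in the one-arm runs.
- Analysis: mixed-model contrast for 12-week change at .01.

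Bias is in SD of change:

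| Mechanism | Drop-out | Bias, log-odds 0.5 | Bias, log-odds 1.2 |
|---|---|---|---|
| Sham only, fully outcome-driven (against CPAP) | 20% | 0.05-0.09 | 0.10-0.18 |
| Same | 10% | 0.02-0.05 | 0.05-0.10 |
| Same | 5% | 0.01-0.02 | 0.03-0.05 |
| Equal in both arms | 20% | at most 0.01 | at most 0.01 |

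If only a quarter of sham drop-out is outcome-driven, the bias is about 0.01-0.05 at 20% drop-out and at most 0.03 at 10%.

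Power at 20%, sham only and fully outcome-driven (log-odds 0.5, then 1.2):

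- Effect 0.74: from 99% to 95-98%, then 86-96%.
- Effect 0.53: from 81-83% to 62-76%, then 40-66%.
- With a quarter outcome-driven, power for 0.74 stays at 97% or more.

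**4. How the check behaves.** Here it is a joint likelihood-ratio test at .05. The plan sets no such rule, so these rates are illustrations only.

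- Baseline characteristics only, 20% drop-out: significant in 5-7% of trials under biased one-arm MNAR, but in 56-100% under baseline-driven MAR, where bias was 0.00.
- With 6-week values added and all drop-out after week 6: significant in 12% and 26% under biased sham-only MNAR, and in 15% and 55% when sham drop-out followed the observed 6-week value, which is MAR with bias 0.00.

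**5. Tipping points.** Shift = (observed d - significance boundary) / fraction missing, with the shift applied to CPAP drop-outs and the standard error held fixed.

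- 20% drop-out, 84 completers per arm: boundary = t(.995, 166) × √(2/84) = 2.606 × 0.1543 = 0.402. For 0.74: (0.74 - 0.402) / 0.20 = 1.69 SD. For 0.53: (0.53 - 0.402) / 0.20 = 0.64 SD.
- 10% drop-out, 105 × 0.9 = 94.5, 94 used: boundary = t(.995, 186) × √(2/94) = 2.602 × 0.1459 = 0.380. For 0.74: 0.360 / 0.10 = 3.60 SD. For 0.53: 0.150 / 0.10 = 1.50 SD.

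The 0.74 is the plan's Aim 1 figure and concerns fructosamine ("our pilot/feasibility study suggests that CPAP improves glycemic control as measured by serum fructosamine"). The 0.53 is Aim 2's detectable effect, used as a smaller-effect case because no effect size is given for A1C.

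**The case against.** The strongest reply is that the plan never says the logistic result alone triggers the MNAR models. It also mentions patterns and covert mechanisms, pattern-mixture models are already named, and the Aim 1 section already states MAR as the basis of the mixed model. A reader might infer that a p-value below .05 is the formal switch. The documents do not support that: the .05 level is for screening data, and no level is attached to the choice of branch. What remains is that every input to the choice is observed data, and no other criterion is given.

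The second reply concerns size, and it largely stands. The larger biases assume that all sham drop-out is outcome-driven, at a 20% rate the plan itself calls conservative. The one documented route is narrower. Its frequency is not given, and excluding people with a near-miss or accident in the last 12 months should make it rarer.

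A reader might also infer that the trial risks a false claim of benefit. If outcome-driven drop-out were confined to the CPAP arm, the bias would be of similar size in favour of CPAP (type I error 1.3-2.6% or 3-9% against a nominal 1%). No part of the documents supports that pattern, so it is an assumption only. The documented direction would make a positive result conservative.

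**Conclusion.** The point holds as one of identifiability. The plan assigns to observed data a decision they cannot make, and it makes the only MNAR analysis conditional on that decision. Confidence in this is high.

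Confidence does not extend to material bias in this trial, because every bias figure rests on an assumed drop-out mechanism. An Aim 1 effect as large as 0.74 is fairly robust at 20% drop-out; an effect near 0.53 is less so. At the 5-10% attrition the plan reports, the bias would be smaller.

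A reader might conclude that the primary mixed model is invalid. It is not: MAR is a reasonable working assumption, and what is missing is a guaranteed account of how far the result depends on it. The change should be made, but it sits at the lower end of that grade.

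**What to change.** Amend Preliminary Analyses in Section C as follows:

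1. State MAR as the working assumption of the primary mixed model.
2. Use the logistic regression only to describe drop-out.
3. Whatever it shows, run the pattern-mixture analysis already named, as a sensitivity analysis of the H1 contrasts: A1C and fructosamine at 6 and 12 weeks, with 12 weeks the main concern. Apply delta adjustments separately by arm, over a range fixed before unblinding, and report a tipping point.
4. Apply it to drop-outs, not to fructosamine left uncollected by design at West Virginia University (Primary Dependent Measures, Aim 1).

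Do not enter post-randomisation variables such as 6-week sleepiness or recorded CPAP use as covariates in the Aim 1 model, since that could adjust away part of the treatment effect. If they are used at all, use them only as auxiliary variables in an imputation step of the sensitivity analysis. That would extend the plan's present limit of imputation to predictor variables, and the text should say so.

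The primary model, the sample size and data collection do not change. The cost is a short passage of SAP text, modest programming and one more sensitivity result to report.

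### The optional baseline adjustment in the Aim 1 repeated-measures model, as its terms are named, would leave the change-from-baseline contrasts essentially unadjusted

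*Combined protocol and SAP*

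**What the plan says.** All the relevant text is in section C, Statistical Analysis, mostly under Data Analysis Plan for Primary Aim 1.

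- **Role of baseline:** "We will consider the baseline value both as an assessment point as well as a possible covariate in analyses".
- **Where the covariate would go:** "Fixed and/or time-dependent covariates (including baseline outcome values) may be included in the repeated measures model as indicated secondarily". The stated purpose is to deal with imbalance between arms or with variables related to the outcome.
- **Model terms:** time is a repeated within-subjects "factor, while treatment assignment will be a fixed, between-subjects factor, with an interaction between time and group". No covariate-by-time term is named, and none is ruled out.
- **H1 test:** "linear contrasts will be specified and estimated when fitting the repeated measures model to compare, relative to baseline values", at 6 and at 12 weeks. Baseline is therefore one of the response visits.
- **Covariance structure:** not fixed in advance. It is chosen after inspection, and "Fit indices will also be used to evaluate the repeated measures models estimated assuming different covariance structures".
- **Status of adjusted models:** Preliminary Analyses says "Covariates/confounders will be included in models secondarily and their effect on the results of primary predictors/factors will be evaluated".

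Analysis Strategy for Aim 2 adopts the Aim 1 approach, so the same wording governs the self-management outcomes.

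**The concern.** The text names one repeated-measures model. It makes baseline a level of the time factor in that model and then lets baseline enter the same model as a covariate. A covariate with one fixed coefficient adds the same amount to a subject's expected value at every visit, so it disappears when baseline is subtracted from a later visit.

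What is at stake is the secondary check on baseline imbalance. Minimization balances step count, previous diabetes education and insulin use, but not baseline A1C or fructosamine, so chance differences in these are possible. A baseline-adjusted analysis that reproduces the unadjusted one would be read as evidence that imbalance does not matter, although the model could not have shown otherwise. The precision that a proper adjustment brings would also be lost. If the analyst tries an unstructured covariance, the fit fails or its fit index means nothing, and fit indices are part of how the structure is chosen.

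**Working it through.** **Inputs.** From Sample Size Justification: 84 completers per group, d = 0.53 on change from baseline, power 0.80, two-sided significance level .01, 20% attrition, 210 enrolled. Assumed, because the documents give no figure: the baseline-to-follow-up correlation r, and equal variances across visits.

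**1. The plan's own figure.** n per group = 2(2.576 + 0.842)²/0.53² = 83.2, so 84 (power 0.805; the noncentral t gives 85, and power 0.795 at 84). 84/0.80 = 105 per group, 210 in total. The figure reproduces, and it is sized on the unadjusted change contrast.

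**2. Cancellation with complete data.** For arm g and visit t the fitted mean is Ȳ(g,t) − b·B̄(g), where B̄(g) is the arm's mean baseline and b the covariate slope. The second term does not depend on t. Hence

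[Ȳ(g,t) − b·B̄(g)] − [Ȳ(g,0) − b·B̄(g)] = Ȳ(g,t) − Ȳ(g,0) for every b.

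The same holds for any time-fixed covariate entered as a main effect only.

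**3. Numerical check.** One simulated data set had 84 per arm, three visits, r = 0.7 and a deliberate baseline imbalance. It was fitted by REML with a random intercept.

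| Model | 6-week | 12-week |
|---|---|---|
| Baseline as response, no covariate | −0.463617 | −0.465940 |
| Same, plus baseline main effect (b = 0.781) | −0.463617 | −0.465940 |
| Same, plus baseline-by-time | −0.360 | −0.371 |
| Follow-up values only, baseline and baseline-by-time as covariates | −0.360 | −0.371 |

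The SE is 0.107193 in both of the first two rows. The gap to the last row at 6 weeks, 0.464 − 0.360 = 0.104, is the adjustment that did not happen. Algebraically, the change contrast minus the covariate-adjusted contrast is −(1 − β)Δ, with Δ the arm difference at baseline and β the slope of follow-up on baseline.

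**4. With dropout** (about 22%, dependent on baseline).

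| Model | 6-week (SE) | 12-week (SE) |
|---|---|---|
| No covariate | −0.4425 (0.1123) | −0.4729 (0.1181) |
| Baseline main effect | −0.4403 (0.1083) | −0.4701 (0.1128) |
| Follow-up only, baseline and baseline-by-time | −0.3368 | −0.3777 |

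The main effect moved the estimate by 0.0022 of a possible 0.1057 (2%) at 6 weeks and by 0.0028 of 0.0952 (3%) at 12 weeks. The reported SE nevertheless fell by about 4%.

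**5. Unstructured covariance.** Subtracting b times baseline from all three visits multiplies the determinant of the residual covariance by (1 − b)². With 168 subjects this adds 168·ln[1/(1 − b)] to the profile log-likelihood. From 182 at b = 0 it reaches 956 at b = 0.99 (182.4 + 168 × 4.605) and 2503 at b = 0.999999. It has no maximum, while the contrasts stay the same at every b.

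**6. What a proper adjustment would bring.** The variance is proportional to 2(1 − r) for the change contrast and to 1 − r² for the adjusted contrast, so the ratio is (1 + r)/2.

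| Assumed r | Variance ratio | Power at 84 per group, d = 0.53 | n per group for 80% power |
|---|---|---|---|
| 0.5 | 0.75 | 0.918 | 63 |
| 0.6 | 0.80 | 0.897 | 67 |
| 0.7 | 0.85 | 0.875 | 71 |
| 0.8 | 0.90 | 0.852 | 75 |
| 0.9 | 0.95 | 0.829 | 79 |

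The comparison is power 0.805 and 84 per group for the unadjusted change contrast.

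**The case against.** The strongest reply is that the plan permits this model without committing to it. The covariate is only possible, its inclusion is optional and secondary, and the plural *analyses* can mean two alternative models. That stands: the text is not a commitment to put baseline on both sides. It does not settle the matter, though. The covariate sentence points to the repeated-measures model itself. If baseline were only a covariate, it would no longer be a visit, the stated contrasts relative to baseline could not be formed, and the plan gives no replacement.

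A second reply is that cancellation is not general. This also stands. A covariate-by-time term, not ruled out, restores the adjustment, and dropout makes cancellation approximate. But the plan names no such term, and the residual movement in step 4 is small.

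A third reply is that an unstructured fit would fail visibly and so mislead nobody. That is fair for that structure. It does not help under a random-intercept or compound-symmetry structure, where the fit runs without trouble.

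A reader might infer more: that the H1 test itself is invalid, that its error rate is inflated, or that the trial is too small. The documents do not support this. Adjusted models are secondary, the unadjusted change contrast is valid under randomization, and the sample size was computed for it. Nor can the gain be sized from the mean test-retest correlation of 0.40 given for the SDSCA: it comes from a self-care questionnaire, and is not a baseline-to-follow-up correlation for A1C or fructosamine.

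**Conclusion.** The point holds for the optional secondary adjustment. Built from the named terms plus a baseline main effect, it cannot adjust the H1 contrasts for baseline imbalance: not at all with complete data, and hardly at all with dropout near the planned 20%. Agreement between adjusted and unadjusted results would carry no information, and the unstructured version cannot be fitted.

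This rests on baseline remaining a response visit and on no covariate-by-time term being added; the plan allows both but states neither. The simulated sizes depend on an assumed correlation of 0.7 and an assumed imbalance, whereas the complete-data cancellation depends on neither. The efficiency forgone, 5% to 25% of the contrast variance for r from 0.9 down to 0.5, is likewise conditional on r.

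The text should be corrected before analysis, but the point does not bear on the lead test.

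**What to change.** In Data Analysis Plan for Primary Aim 1, and so for Aim 2 by reference, state that baseline has one role in any given model. Remove baseline outcome values from the permitted covariates of the model that has baseline as a time point. Then specify the baseline-adjusted analysis as one of the following:

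1. Only the 6- and 12-week values are responses, with baseline and baseline-by-time as covariates, and the arm difference is tested at each week.
2. Baseline stays a response, the two arms share a common baseline mean, and there is no baseline covariate.

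The cost is a few sentences in the analysis section. The data, visits, software and sample size stay as they are.
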